3.2. Exclusion Criteria

- 1. Subjects who have already had cataract surgery with a Toric or multifocal Intraocular Lens.
- 2. Subjects who have already had cataract surgery with a Bausch and Lomb monofocal intraocular lens model LI61A0 (with a lens power below 18.0 D and greater than 23.0 D) or model LI61SE (with a lens power below 18.0 D and greater than 22.5 D).
- 3. Subjects who were treated with an IOL off-label.
- 4. Subjects who have MRSE of less than -0.5D and more than +3.0D
- 5. Subjects who have more than 1.5D of corneal cylinder
- 6. Subjects whose continuous curvilinear capsulorhexis was less than 5mm or more than 6.0 mm in size at the time of IOL surgery.
- 7. Subjects who had cataract surgery less than 6 months from the planned date of the IOPCL surgery.
- 8. Subjects with anterior capsule fibrosis and phimosis that in the opinion of the investigator may confound the outcome or increase the risk to the subject.

- 9. Acute, chronic or uncontrolled systemic or ocular disease that in the opinion of the investigator would increase the operative risk or confound the outcome(s) of the study.
- 10. Any corneal abnormality, other than regular corneal astigmatism that in the opinion of the investigator would confound the outcome(s) of the study.
- 11. Clinically severe corneal dystrophy (e.g., epithelial, stromal, or endothelial dystrophy).
- 12. Microphthalmos.
- 13. Previous retinal detachment.
- 14. Recurrent severe anterior or posterior segment inflammation of unknown etiology.
- 15. Iris neovascularization.
- 16. Uncontrolled glaucoma.
- 17. Aniridia.
- 18. Optic nerve atrophy.
- 19. Damaged or incomplete zonules.
- 20. Known history of pseudoexfoliation.
- 21. Medications that, in the opinion of the investigator, may confound the outcome or increase the risk to the subject (tamsulosin hydrochloride (Flomax)) or other medications with similar side effects (floppy iris syndrome).

4. Subject Entry

The investigator or qualified site personnel will explain the study purpose and procedures necessary to allow the subject to decide whether to give informed consent and will explain the subject's responsibilities. The subject's willingness and ability to meet the follow-up requirements will be determined. Preoperative exam will be conducted after the subject provides informed consent (see Appendix 1).

After it has been determined that all inclusion/exclusion criteria have been met the subject will be enrolled into the study.

5. Treatment Plan

Duration of Study Treatment – 12 Months (330-420 days)

All patients will receive the investigator standard postoperative regimen for cataract surgery.

6. Lens Power Selection

All subjects will be implanted with a +3.0D IOPCL. Implanting this lens power in a subject with a baseline MRSE of -0.50D to +3.0D will give subjects a myopic refractive change allowing for an improvement in uncorrected vision at distance, intermediate, or near depending on the subject's preoperative refraction.

7. Ophthalmic Visco-surgical Device (OVD)

ProVisc® (sodium hyaluronate) Alcon, will be used as a surgical aid when inserting the AccuraSee IOPCL.

8. Position of IOL Haptics and IOPCL Incision Location

[figure not shown]
After adequate dilation, the surgeon will determine and record the orientation and angular dimensions of the haptics of the in-place IOL. The surgeon will also determine the degree and angular dimensions of the anterior capsule coverage in the planned region of the tri-haptic tunnel formation. The surgeon will determine if there is adequate coverage of the anterior leaflet capsule at the edge of the underlying IOL where the haptics of the IOPCL will reside. Adequate coverage is defined as greater than or equal to 0.5 mm of anterior leaflet of capsule above where the haptics will reside.

These notations will be transferred to the Pre-Operative case report form to document the position of the IOL haptics and IOPCL incision location.

9. Surgical Technique: Insertion and Removal Instructions

Video recordings will be created for each subject surgery and provided to the Sponsor for future review and assessment.

The AccuraSee Intraocular Pseudophakic Contact Lens (IOPCL) is designed to modify the refractive error of a pseudophakic eye. Using a novel tripod haptic design (see figure 1) placed within 3 channels created under the anterior leaflet of the capsular bag the optic is centered and secured over the existing posterior chamber intraocular lens (PCIOL). Each haptic has a ridge that acts as a pawl on the bottom that catches and locks onto the IOL optic edge. This pawl aids in both centering the IOPCL on the PCIOL optic as well as securely seat the haptic while contained under the anterior leaflet of the capsular bag. The lens is 4.5mm in diameter with the 3 extending haptics arranged in an isosceles pattern to avoid interference with the haptic/optic junctions of the existing PCIOL. The apex and leading tab is marked R to identify the anterior surface of the lens and prevent inverse implantation and help guide positioning onto the existing PCIOL. When the lens is right-side up the R should be visible and properly oriented when implanting the IOPCL.

INSTRUCTIONS FOR USE

ACCESSS TO THE ANTERIOR CHAMBER

Under sterile technique create a 2.5 mm wide beveled, self-sealing incision from the clear corneal limbus into the anterior chamber directly across from the planned placement of the leading haptic (denoted with the "R" inversion mark). Construct a 1.5 mm paracentesis directly across from initial 2.5 mm incision, with option (Surgeon preference) to create an additional paracentesis in any chosen plane to aid in IOPCL positioning. The IOPCL should be free from interfering with the optic-haptic junctions of the already seated in-the-bag PCIOL.

IOPCL HAPTICS CLEAR OF IOL HAPTICS

Figure 2 - ALIGNMENT OF THE AccuraSee IOPCL

PREPARATION OF THE CAPSULAR CHANNELS

Mark the cornea with provided cornea marker, isolating the leading haptic mark. The leading haptic mark is to be placed on a lone side of the underlying PCIOL separated by the optic-haptic junction. The projected markings are to help guide the surgeon as to where the three anterior leaflet 1.5 mm channels will be created to receive the IOPCL haptic system. With ProVisc in the anterior chamber using the Capsule Separator, create 3 channels in the appropriate positions (See figure 2) under the anterior leaflet of the capsular bag. These channels should be 1.5mm wide straddle the radial cornea mark and reach a length peripherally to just beyond the edge of the underlying IOL. The 'R' haptic is to be positioned between the two IOL haptics and the other two haptics on the other side between the two haptics, as shown. Through the initial 2.5 mm incision advance spatula across iris plane to construct a liberal 1.5 mm size tunnel to house leading haptic. Make sure to advance spatula beyond the edge of the underlying IOL about 2 mm in order to allow the leading edge of the IOPCL haptic to seat unrestricted. Suggestion: Separate leading edge of anterior capsule approximately 2mm either side of tunnel to ease introduction of IOPCL haptic leading edge. Utilizing the paracentesis, introduce and advance the spatula across iris plane and create a sweeping dissection of anterior leaflet from one corneal mark to the other. Once again make sure you allow a 2 mm gap beyond the edge of the IOL limited to the area where the trailing haptics will be introduced and rest. If cortical material is present, break up and remove any loose cortical material. It will be necessary to create a space approx. 2.0mm beyond the edge of the existing PCIOL to allow space for the tip of each IOPCL haptic to properly seat beyond the optic edge of the existing PCIOL. In an effort to further dissect or elevate anterior leaflet from capsule, you may choose to introduce viscoelastic under leading tunnel and swept area of anterior leaflet capsule.

INSERTION OF THE IOPCL

Load the IOPCL into the LIOLI-22 injector according to the manufacturer's instructions.

CAUTION: It is important to place the IOPCL in the center of the cartridge chamber so that the haptics are well away from the edges of the flaps when they are folded closed. Otherwise the haptics may get caught between the flaps and become torn when the plunger is pressed to advance the IOPCL in the injector. It is also suggested that additional ProVisc be placed at the posterior entrance to the cartridge so as to provide a buffer between the plunger and the folded IOPCL. It is also suggested while closing the cartridge to press down on the center of the optic to assure the haptics remain free of the cartridge flap. Carefully push the plunger forward to ensure that the silicone tip correctly enters the loading chamber, while making sure not to capture one of the haptics between the plunger and the cartridge wall. Continue to push the tip until the inner spring begins to compress. Pull the plunger back a few millimeters and then push it forward again. This step ensures that the lens is correctly grasped.

Inject the IOPCL with the leading haptic forward denoted by the "R" inversion mark into the anterior chamber of the eye, thru the previously placed 2.5mm cornea incision. Using angled intraocular manipulating hooks such as Sinskey or collar button, rotate the IOPCL to line up the haptics with the previously placed channels and guide the haptics into each of the 3 channels. Once distal haptics are firmly seated, grasp leading haptic with surgical tool of choice through either the 1.5 mm paracentesis incision or initial 2.5 mm incision and advance the leading haptic under the anterior leaflet into awaiting 1.5 mm tunnel. If needed introduce a second instrument through paracentesis incision to aid in lifting edge of capsule to ease the advancement of the leading haptic into created tunnel. After placing each haptic, confirm that it is beneath the anterior flap, properly seated and has captured the edge of the existing PCIOL. Ensure that there is no interference between the haptics of the pre-existing PCIOL and the IOPCL. The optic of the IOPCL should be flat and well centered to the existing PCIOL. Irrigate and aspirate all residual ProVisc and any displaced material from the anterior chamber. Once all three haptics are resting unrestricted, using light rocking motion, manipulate the IOL to assure the tri-haptic system has a uniform grasp to the edge of the underlying IOL. Finally, confirm that the IOPCL remains well centered with the haptics well secured under the anterior leaflet capsule. Hydrate and close the incision per your normal anterior chamber procedures.

REMOVING CELLULAR MATTER (OPACIFICATION) BETWEEN THE IOL AND IOPCL

Using an irrigating cannula and BSS loosen the cortical/cellular material between the two lenses from the periphery, followed by removal with a coaxial/aspiration (I/A handpiece). Alternatively utilize a bi-manual I/A system with separate irrigation and aspiration handpieces. These small handpieces can be introduced through two 1.0 mm paracentesis incisions and can easily fit between the two lenses delivering irrigation from one side and aspiration from the opposite side to remove any cortical or interlenticular cellular material place a small amount of ProVisc® within the angle of the anterior chamber to stabilize the chamber while allowing for free flow of BSS fluid. Use a straight 27 gauge

cannula on a 5cc syringe filled with BSS to vigorously irrigate the space between the two lenses. If for some reason the vigorous irrigation did not remove all the debris from the inter-lenticular space carefully release the haptic/tabs of the IOPCL closest to the location of the debris and continue to irrigate. If this approach is unsuccessful consider removing the IOPCL, irrigate the surface debris on the surface of the IOL and replace it with another IOPCL. If the debris attached to the surface of the IOL remains adhered after the final attempt to irrigate do not introduce a new IOPCL. At the conclusion of the case, please record in detail on the CRF every and all steps taken to remove the cellular material between the two lenses.

REMOVAL OF THE IOPCL

Re-open the initial incisions or create new access into the anterior chamber if they have healed. With ProVisc in the anterior chamber use a Sinskey hook or similar instrument to disengage the three IOPCL haptics from their respective channels. Place a small amount of ProVisc between the IOPCL and existing PCIOL to separate them apart. Using microforceps thru the 2.0 mm wide incision, grasp the anterior and posterior surface of the IOPCL and remove it through the incision. The IOPCL is flexible and will fold and achieve a "taco" form for removal in one piece. After explantation of the complete IOPCL, assess the lens surface of the existing PCIOL for any damage. If any damage is noticed on the existing PCIOL particularly on its lens surface, please record this on the IOPCL removal Case Report Form. Remove the remaining ProVisc, irrigate and close the wound per your normal IOL procedures.

Please return the removed IOPCL to the Sponsor for damage assessment.

YAG CAPSULOTOMY

A Nd:YAG capsulotomy is not allowed to treat opacity between the IOPCL and PCIOL after implanting the IOPCL. Irrigation should be performed to remove the cellular matter from the lens(es) See page 10 for irrigation instructions

If clinically significant PCO is observed on the posterior side of the PCIOL, treatment using standard Nd:YAG capsulotomy is allowed. Nd: YAG capsulotomy should not be performed prior to 12 weeks post IOPCL implantation.

10. Examination Schedule

Subjects will be examined and evaluated according to the following schedule of visits.

Form OA – Pre-Operative Operative (Form OB)

Form 1 (1 to 2 days postoperative)

Form 2 (7-14 days postoperative)

Form 3 (30-60 days postoperative)

Form 4 (120-180 days postoperative)

Form 5 (330-420 days postoperative)

10.1 Post-Explantation IOPCL Examination Schedule

Following the removal of the IOPCL subjects will be evaluated according to the following schedule of visits.

Form 1X (1-2 days post-removal)

Form 2X (7-14 days post-removal)

Form 3X (30-60 days post-removal)

Form 4X (120-180 days post-removal)

Form 5X (330-420 days post-removal)

10.2 Unscheduled / Interim Visits

Additional visits may be scheduled as deemed necessary by the investigator, to ensure the safety and well-being of the subject.

11. Clinical Assessments

All parameters will be recorded for both eyes at baseline (pre-operative). Measurements will be recorded for the study eye at postoperative and post-removal visits. See Appendix 2A schedule of visits (pre and post-operative visits) and Appendix 2B (post-removal visits). See Appendix 3 for clinical assessment instructions

- Inclusion/exclusion criteria: Preoperative
- Medical history: Preoperative
- Demographics: Preoperative
- Patient Informed Consent: Preoperative
- Measurements: Make and Model # of Equipment Preoperative
- Axial Length & Keratometry Preoperative
- Capsulorhexis Size at the time of IOL surgery: Preoperative
- Position of IOL Haptics and IOPCL Incision Location: Preoperative
- Mesopic and Photopic Pupil size measured by Pupilometer: Preoperative

- Predicted Post-Op Refraction: Preoperative
- Pseudophakic IOL power with make and model number: Preoperative
- Spatial Visualization between the PCIOL and IOPCL Using UBM: 30-60 days, 120-180 days, 330-420 days, Interim.
- Recording of the IOPCL Surgical Procedure: Operative
- UCDVA: Uncorrected Distance Visual Acuity Preoperative, 7-14 days, 30-60 days, 120-180 days, 330-420 days. Interim
 - Post-removal, 7-14 days, 30-60 days, 120-180 days, 330-420 days. Interim
- UCIVA: Uncorrected Intermediate Visual Acuity Preoperative, 7-14 days, 30-60 days, 120-180 days, 330-420 days. Interim
 - Post-removal, 7-14 days, 30-60 days, 120-180 days, 330-420 days. Interim
- UCNVA: Uncorrected Near Visual Acuity Preoperative, , 7-14 days, 30-60 days, 120-180 days, 330-420 days, Interim.
 - Post-removal, 7-14 days, 30-60 days, 120-180 days, 330-420 days. Interim
- BCDVA: Best Corrected Distance Visual Acuity Preoperative, 7-14 days, 30-60 days, 120-18 days, 330-420 days, Interim
 - Post-removal, 7-14 days, 30-60 days, 120-180 days, 330-420 days, Interim
- Manifest Refraction: Preoperative, 7-14 days, 30-60 days, 120-180 days, 330-420 days, Interim
 - Post-removal, 7-14 days, 30-60 days, 120-180 days, 330-420 days, Interim
- Auto-refraction: Preoperative, 7-14 days, 30-60 days, 120-180 days, 330-420 days. Interim
 - Post-removal, 7-14 days, 30-60 days, 120-180 days, 330-420 days, Interim.
- Slit Lamp Examination: Preoperative, 1-2 days, 7-14 days, 30-60 days, 120-180 days, 330-420 days. Interim
 - Post-removal, 1-2 days, 7-14 days, 30-60 days, 120-180 days, 330-420 days, Interim

- Sun Grading System: 1-2 days, 7-14 days, 30-60 days, 120-180 days, 330-420 days. Interim
 - Post-removal, 1-2 days, 7-14 days, 30-60 days, 120-180 days, 330-420 days, Interim
- Gonioscopy: 7-14 days, 30-60 days, 120-180 days, 330-420 days. Interim
 - Post-removal, 1-2 days, 7-14 days, 30-60 days, 120-180 days, 330-420 days, Interim
- Intraocular Pressure: Preoperative, 1-2 days, 7-14 days, 30-60 days, 120-180 days, 330-420 days, Interim

Post-removal, 1-2 days, 7-14 days, 30-60 days, 120-180 days, 330-420 days, Interim

- Quality of Vision (QoV) Questionnaire: Preoperative, 30-60 days, 120-180 days, 330-420 days.
 - Post-removal, 30-60 days, 120-180 days, 330-420 days, Interim
- Adverse Events and Complications: Operative, 1-2 days, 7-14 days, 30-60 days, 120-180 days, 330-420 days, Interim
 - Post-removal, 1-2 days, 7-14 days, 30-60 days, 120-180 days, 330-420 days, Interim

12. Definitions of Adverse Events

Serious Adverse Event (SAE): An Unanticipated Adverse Device Effect associated with the device (UADE) is considered to be "serious" in any of the following categories and should be reported to OnPoint Vision Inc. OnPoint Vision Inc. within 5 working days after the investigator first learns of the event.

- Results in death
- Life-threatening
- Hospitalization greater than 24 hours
- Persistent and/or significant disability/incapacity
- Sight-threatening

Intraoperative Adverse Events

- > Hyphema
- > IOL Dislocation
- > Retinal Tear
- ➤ Vitreous/Subchoroidal Hemorrhage
- > Vitrectomy

- > Retinal Detachment
 - o Rhegmatogenous Retinal Detachment
- Ruptured Capsular Bag with or without Vitrectomy
- Ruptured or Damaged Zonules
- > IOL Lens Dislocation from the Bag
 - o Partial
 - o Complete
- ➤ Excessive length of time in the eye to deliver (longer AccuraSeeTM than 30 minutes)
- > Failure to Implant IOPCL

Postoperative Adverse Events

- > Endophthalmitis
- ➤ Toxic Anterior Segment Syndrome (TASS)
- > Chronic Anterior Uveitis
- > Hyphema
- > Hypopyon
- > Implantable Pseudophakic Contact Lens Dislocation
- Cystoid Macular Edema
 - Clinically Significant Cystoid Macular Edema with reduction in BCDVA of 20/40 or worse at Form 3 (1-2months post op) or later
- Pupillary Block
- Mechanical Pupillary Block
- > Retinal Detachment
 - o Rhegmatogenous Retinal Detachment
- ➤ Iridectomy for Pupillary Block
- ➤ Malpositioned/Misaligned Optics (IOPCL not centered over PCIOL)
 - o Early[1]
 - o Late[2]
- Unseated IOPCL haptic tabs (One or more haptic tabs not securely attached to the PCIOL)

- > Post Nd:YAG Posterior capsulotomy event
- > Lens Optical Performance
- Mechanical Failure
- Vitreous Aspiration for Pupillary Block
- Corneal Stroma Edema
 - Corneal Edema with BCDVA of 20/40 or worse at Form 3 (1-2M post-op) or later
- > Iritis present at 1-month or later
- Macular Edema present at 1-month or later
- > Raised IOP requiring treatment
 - Raised IOP, greater than 10 mmHg above baseline and to a minimum of 25 mmHg.
- ➤ Iris Chafing
- > Iris Trauma and/or Damage
- > Iris Transillumination Defects
- > Pigment Dispersion
- > Pseudophacodonesis or Evidence of Zonular Trauma/dehiscence
- > Inter-device opacification or fibrosis between the PCIOL and IOPCL
- > Other

```
[1]Early – prior to Form 4 visit window (i.e., < 120 days)
[2]Late – At 120 days or later
```

Note: Secondary Surgical Intervention(s) (SSI) may be necessary to resolve any of the adverse events identified above. If an SSI is conducted in the trial, the details of the SSI and corresponding reason for SSI will be documented on the SSI CRF.

Examples of Secondary Surgical Interventions

- ➤ Irrigation of IOPCL/IOL Interface
- > Exchange
- ➤ Reposition of the same Implantable Pseudophakic Contact Lens
- ➤ Removal

13. Adverse Experience and Complication Reporting

Throughout the course of the proposed study, all efforts will be made to remain alert to possible adverse experiences or untoward findings. If adverse experiences occur, the first concern will be the safety and welfare of the subject and appropriate medical intervention will be made. Any adverse experiences observed by the investigator or reported by the subjects, whether or not ascribed to the investigational procedure or device, will be recorded on the subjects' adverse event case report form. A new adverse event case report form is used for each adverse event or adverse event related visit.

Any serious adverse events (SAEs) and unanticipated adverse device events (UADE), whether ascribed to the investigational device or not, will be communicated as soon as possible to OnPoint Vision Inc. OnPoint Vision Inc. and to the IRB. These reports must be confirmed in writing within 5 working days of learning of the occurrence. Any subjects who are terminated from the study due to adverse experiences will be followed and documented until their medical outcome is determined, and a written report provided to OnPoint Vision Inc. by the investigator.

14. Concomitant Medications/Therapy

The investigator may prescribe medications and therapy as deemed beneficial for the subject.

15. Data Collection

Data will be collected using case report forms (see Appendix 8). Completed case report forms will be scanned to the sponsor within seven days of the study visit.

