7.5.4 Adverse Events

For each adverse event, number and percent of eyes reported with the event will be summarized at each scheduled visit (including intraoperatively) and during the study (i.e. cumulative and persistent).

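### Protocol Section 12 defines an SAE as a device-associated unanticipated effect, which contradicts Section 13 and leaves some serious events with no stated prompt route to the IRB

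*Protocol*

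**What the plan says.** Protocol Section 12 has one entry under the SAE heading: "An Unanticipated Adverse Device Effect associated with the device (UADE) is considered to be 'serious' in any of the following categories". Five categories follow, one of them "Sight-threatening". Such events go to the sponsor "within 5 working days after the investigator first learns of the event". No other definition of an SAE appears in the Protocol or SAP text supplied.

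The same section then lists named intraoperative and postoperative adverse events. "Endophthalmitis" is in the postoperative list, and "Rhegmatogenous Retinal Detachment" is in both lists, under retinal detachment.

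Protocol Section 13 sets the reporting rule. It covers serious adverse events "and unanticipated adverse device events (UADE), whether ascribed to the investigational device or not, will be communicated as soon as possible" to the sponsor and the IRB, with written confirmation within 5 working days. It also says that every adverse experience, whatever its cause, is recorded on the adverse event case report form.

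Protocol Section 15 has completed case report forms scanned to the sponsor within seven days of the study visit.

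SAP Section 7.5.4 plans this: "For each adverse event, number and percent of eyes reported with the event will be summarized at each scheduled visit", and also over the whole study. The SAP neither defines nor summarises SAEs as a class.

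**The concern.** Section 12 builds two conditions into the term SAE that have nothing to do with how serious an event is: it must be unanticipated, and it must be associated with the device. Section 13 then uses the same term as if neither condition applied. It names SAEs alongside UADEs as a second class, and it sets attribution aside.

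Prominent among the serious events to be expected after an intraocular procedure are those that the protocol already lists. A coordinator who works from the definition could reasonably conclude that a sight-threatening endophthalmitis is an adverse event but not an SAE, and so does not trigger the prompt report. What is at stake is how quickly the IRB, and to a lesser degree the sponsor, hears of such an event in a first small implant series at three centers.

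**Working it through.** No arithmetic applies. The check sets the sections side by side and follows one event through them.

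**1. Direct conflict on attribution.** Section 12 requires association with the device. Section 13 requires reporting "whether ascribed to the investigational device or not, will be communicated as soon as possible". If every SAE is device-associated by definition, Section 13's phrase can add no event to the SAE class. This conflict needs no view on what is anticipated.

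**2. Conflict on the number of classes.** Section 13 names SAEs and UADEs as two things to report. Under Section 12 every SAE is a UADE, so the first class lies wholly inside the second and naming it adds nothing.

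**3. Which serious events are left out.** Take an event that meets one of the five categories, and apply each section literally:

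| Event meeting a seriousness category | SAE under Section 12? | UADE? | Does attribution matter under Section 13? |
|---|---|---|---|
| Unanticipated, device-associated | Yes | Yes | No |
| Unanticipated, not device-associated | No | No | No |
| Foreseen, device-associated | No | No | No |
| Foreseen, not device-associated | No | No | No |

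Only the first of the four rows is an SAE. The second and fourth rows fail on attribution, which Section 13 says should not matter. The third fails on anticipation alone.

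**4. Where the listed events fall.** The protocol defines neither anticipated nor unanticipated, and the headings of the lists in Section 12 do not use either word. That endophthalmitis or retinal detachment belongs in a foreseen row is an inference from its being named in advance. It is a sound inference, but the text does not state it.

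**5. What happens to an event outside both classes.** Section 13 attaches prompt notice to the sponsor and IRB only to SAEs and UADEs. Any other event goes on the adverse event form, which reaches the sponsor under the seven-day rule in Section 15. For the sponsor, 5 working days usually span about 7 calendar days, so for an event seen at a visit the written deadlines are close. The clocks do start differently: Section 12 counts from when the investigator learns of the event, Section 15 from the study visit. For the IRB, Section 13 gives such an event no route.

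**6. Does the looser reading help?** The sentence in Section 12 could be read as saying only when a UADE counts as serious. The protocol would then contain no definition of an SAE for Section 13 to use. Either reading needs repair.

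**7. Does the analysis change?** No. SAP Section 7.5.4 tabulates each event by eye, whether or not it is called serious.

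**The case against.** The case against giving this much weight is substantial, and most of it stands.

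- **The data are safe.** Every adverse experience is recorded regardless of attribution, with a new form for each event, and every event has its own line in the SAP tables.
- **Other safeguards do not use the term SAE.** The suspension rule under Stopping Rules has its own definition of a severe ocular injury. A subject terminated because of an adverse experience requires a written report to the sponsor.
- **Section 13 shows the intent.** An experienced investigator would probably report a sight-threatening event whatever Section 12 says.
- **Some material was not supplied.** The case report forms and the investigator responsibilities are listed as appendices. An adverse event form with its own seriousness field would reduce the practical effect.

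These points limit the consequence. They do not remove the contradiction, and a safety-reporting rule should not depend on readers following the intent over the definition.

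A reader might also infer stronger claims that the documents do not support:

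- **That a reported SAE rate would be biased low**, by 10 percentage points for each omitted event (1 of at most 10 eyes). The SAP plans no SAE rate. Even if it did, two omitted events in one eye, or one in an eye already counted, would not each cost 10 points.
- **That all 38 named events (11 intraoperative and 27 postoperative) are lost SAEs.** The lists include failure to implant, a long delivery time and pigment dispersion. Many of the 38 would not normally meet a seriousness category, and the documents do not say how many would.
- **That a listed event can never be an SAE.** The protocol does not say that naming an event makes every severity of it anticipated.

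**Conclusion.** The point holds as a contradiction in the reporting rule. Section 12's only definition makes an SAE a device-associated UADE, while Section 13 treats SAEs and UADEs as separate classes to be reported regardless of attribution. Followed literally, a serious event that is foreseen or not device-associated falls outside both classes. It has no stated prompt route to the IRB, and it reaches the sponsor only through the routine form.

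The conflict over attribution and over the two classes rests on the text alone. The extension to endophthalmitis, retinal detachment and similar events assumes that an event listed in advance counts as anticipated, and that no unsupplied appendix says otherwise.

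The size is one of classification and speed of reporting. No event count, rate or planned table changes, so no bias figure should be attached. It should be corrected because it concerns safety reporting and the correction is nearly free.

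**What to change.** Reconcile Protocol Sections 12 and 13:

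- **SAE:** define it as any adverse event that meets one of the five categories already in Section 12, whether or not it was anticipated and whatever its relation to the device.
- **UADE:** define it in a separate entry, and say there what makes an event unanticipated, including how the listed events are to be treated.
- **Reporting:** keep Section 13's existing terms for both classes (prompt notice to the sponsor and IRB, and written confirmation within 5 working days), and have Section 12 refer to them.

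The cost is a short wording change and possibly a few more expedited reports, in a study of at most 10 eyes. Check the adverse event case report form against the new definitions at the same time. An SAE row in SAP Section 7.5.4 would be a convenience; its absence is not part of the error.
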